software automatically scores blood pressure readings to calculate average daytime, nighttime, and diurnal systolic, and diastolic blood pressure, hyperbaric index, blood pressure variability, and dipping status (BP fall > 10% from daytime levels). Prior research demonstrates high sensitivity and specificity of ABPM (specifically the hyperbaric index, an index of BP load on organs, blood pressure variability, and dipping status) in the early detection of hypertension. Peripheral blood will be collected via venipuncture before and after the 8-week mindfulness or treatment as usual interval. Samples will be de-identified and stored for future research purposes. (Participants will consent to the collection and banking of blood using a separate consent form.) Research ultrasonography assessments will also be performed before and after the 8-week mindfulness intervention or treatment as usual. The collection of maternal and fetal ultrasound findings will allow evaluation of maternal uterine artery Doppler parameters, placenta size, fetal growth velocity rate and fetal Doppler parameters among the two study groups. Diagnoses of hypertensive disorders will be collected via medical chart review and rates of recurrence will be compared across groups. We will conduct linear mixed effects models to evaluate changes in blood pressure (dependent variable) according to time, group, and time x group interaction (independent variables).

Phase 3: Qualitative Evaluation of Feasibility and Acceptability. Following the intervention, women will be asked to complete in-depth qualitative interviews to solicit feedback on the intervention. Feedback from qualitative interviews will be used to identify patterns and themes in participants' responses that will then be used to further tailor and refine the phone-delivered MT intervention for pregnant women with histories of hypertensive disorders of pregnancy in preparation for a future fully-powered RCT.

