Recruitment. A sample of 30 pregnant women, ages 18-40, before 20 weeks' gestation will be recruited into the study. Pregnant women from OBGYN clinics and practices will be recruited through identification of eligible women through chart review. Women will also be recruited through placements of posters and brochures. Other recruitment sites are: hospital websites, various community sites and community groups, community health care groups and community-based newspapers. Interested participants will be contacted by study staff and initial screening will take place by telephone.

Inclusion/Exclusion Criteria

Inclusion/exclusion criteria: ≥ 18 years old, singleton pregnancy, English speaking, <20 weeks' gestation at enrollment, history of a hypertensive disorder, and no current engagement in mindfulness training (defined as weekly yoga, mindfulness exercises (including on-line), or meditation). Women will be asked to complete a baseline visit remotely to obtain background information on maternal characteristics and medical conditions in pregnancy. Following the baseline session, women will be randomized to phone-delivered MT intervention or to treatment as usual. Randomization will be stratified based on antihypertensive medication use (yes/no), if necessary.

Procedures

Initial Telephone Screening. Interested pregnant women will complete a telephone screen including questions to assess inclusion/exclusion criteria. Visit 1 will then be scheduled with interested participants who meet initial inclusion criteria.

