Following the baseline visit, all eligible and enrolled participants will be instructed to complete ambulatory blood pressure monitoring for 24 hours. Blood pressure will be assessed using *ambulatory blood pressure monitoring* (ABPM, ScottCare device). This validated device (Zawadzki, Vandekar et al. 2013) can measure BP every 30 minutes for 24 hours. ScottCare software automatically scores blood pressure readings to calculate average daytime, nighttime, and diurnal systolic, and diastolic blood pressure, hyperbaric index, blood pressure variability, and dipping status (BP fall > 10% from daytime levels). Participants will be paid \$50 for completing blood pressure monitoring.

Peripheral blood draw and specimen banking. SUSPENDED DURING COVID19 PANDEMIC. Before randomization, women will be asked to provide a peripheral blood sample for specimen banking. We will make every effort to time the peripheral blood draw with clinical blood draws in order to minimize participant burden. Participants who consent to specimen collection and banking will have 10mL (< 1 tablespoon) of blood collected via venipuncture at Lifespan Laboratories. Blood samples will be identified only by the participant ID and stored at -80° C at the RISE building (TMH) for later analysis. Participants will not receive the results of the blood draw. This information is included in the informed consent form.

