Research Ultrasound. SUSPENDED DURING COVID19 PANDEMIC. We will make every effort to time the research ultrasound with clinical ultrasounds in order to minimize participant burden. The first research ultrasound before randomization will occur with, or after, participants have their clinical anatomy scan. Before each research ultrasound, participants will be read a “script” that emphasizes that research ultrasounds do not take the place of clinical ultrasounds. For research ultrasounds, participants will be placed on the ultrasound bed onto their back in a semi-recumbent position, slightly tilted toward their left side. For the research studies, we will use ultrasound devices currently in use for clinical evaluations. We will record fetal heart rate, fetal position, placental position and size, and amniotic fluid index according to standard clinical protocols. Next, we will record fetal biometric parameters and Doppler measurements of maternal and fetal blood vessels. If the following abnormal findings are detected on the research ultrasound, the OB/GYN provider will be notified: 1) fetal anomalies, 2) estimated fetal weight below 10%, 3) abnormal umbilical blood flow, 4) abnormal levels of amniotic fluid, and 5) absent fetal heart rate. Participants will not receive the results of the research ultrasounds. This information is included in the informed consent form.

Randomization. All participants will receive usual prenatal care, which may include intervention to prevent or treat hypertension during gestation. Following the completion of the baseline session, participants will be randomized to treatment group (mindfulness training + treatment as usual, or treatment as usual) using a stratified randomization approach (stratified by hypertension medication use).

Mindfulness Training Intervention + Treatment as Usual. Interested and eligible participants from the Baseline Assessment will be invited to take part in an 8-week phone-delivered mindfulness intervention, in addition to continuing to attend usual prenatal care appointments. Each intervention session will last approximately 30 minutes (4 hours of total intervention) and will be scheduled for a time that is convenient for the participant. Mindfulness training sessions will occur once per week. Sessions

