will be led by an experienced mindfulness instructor, and participants will have the same instructor throughout the intervention. The 30 minutes will include 20 minutes of intervention and 10 minutes for addressing participants' questions and scheduling subsequent sessions. Mindfulness training modules will include awareness of breath, body scan meditation, and sitting and movement meditations. Women will be provided with recordings of mindfulness exercises to use for practice between sessions. Women will be asked to practice mindfulness activities daily in between sessions. Women will be provided with audiotapes that will guide their mindfulness exercises. We will ask that women practice for 15 minutes each day, and record the date and duration of their practice. With participant permission, intervention sessions will be audiotaped for the purpose of assessing treatment fidelity. A research assistant will contact the participant between sessions to ask about any problem or discomfort participants might be experiencing during and between the training sessions, as well as to ask about any problem or difficulty they are having attending prenatal care appointments.

Treatment as Usual. Participants randomized to the treatment as usual condition will continue to receive their regularly-scheduled prenatal care, which may include interventions to prevent or treat hypertension during pregnancy. A research assistant will check in with the participant each week to ask if they have been to any prenatal care appointments, and if so, the number and length of time spent at each.

Repeat Ambulatory Blood Pressure Monitoring. SUSPENDED DURING COVID19 PANDEMIC. All participants will repeat the 24-hour blood pressure monitoring after approximately 8 weeks from enrollment or following completion of the mindfulness intervention, if applicable. The procedures for ambulatory blood pressure monitoring are identical to those that were completed prior to randomization (see above). Participants will be paid \$50 for completing blood pressure monitoring.

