The results of the proposed study will provide preliminary evidence on the feasibility and acceptability of a phone-delivered mindfulness training intervention for pregnant women at risk for hypertension disorders. Results will also provide evidence on the effectiveness of the intervention at reducing psychological symptoms of distress in pregnancy. Finally, results may provide preliminary evidence on the usefulness of such interventions on reducing rates of hypertension in at-risk women. We expect that these benefits will outweigh potential risks to participants.

Data and Safety Monitoring Plan:

[name] will have primary responsibility for monitoring all participants. Any adverse events, breaks of confidentiality, or any other data or safety issues that arise will be immediately brought to the attention of the RIH IRB. [name] will be responsible for completing an Adverse Events Form should an event occur. She will report Serious Adverse Events to the IRB within 24 hours of having received notice of the event. Adverse event reports will be reviewed annually with RIH IRB to ensure participant safety. In the

event that a study participant endorses suicidal ideation during an interview, the interviewer will complete a lethality assessment, will consult with the PI to formulate a course of action, and, with written permission, will consult with the participant's care provider. Appropriate intervention or follow-up care will be arranged with the treating clinician or, if hospitalization is required, through emergency services at Butler, The Miriam, or Rhode Island hospital.

Statistical Approach

Randomization. We will use a stratified randomization procedure to assign participants to mindfulness training vs. usual care based on medications for hypertension. The randomization scheme will be generated based on a permuted block randomization procedure with small random sized blocks. Randomization will be stratified by hypertension medications (yes/no).

Sample size considerations. The proposed sample size was estimated to have sufficient power to assess feasibility and acceptability, as well as to provide a reasonable sample with which to estimate effect sizes and confidence intervals for secondary outcomes. We propose to enroll 30 participants in a 1:1 ratio to mindfulness training and usual care. With a two-sided alpha-level of 0.05, we will have more than sufficient power (>80%) to detect acceptability differences in the small-medium range, $d=0.45/w=.2$.

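### The planned blood pressure model is valid but leaves the baseline group difference free; a common baseline mean would usually narrow the intervals a little, at no cost in data

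*Combined protocol and SAP*

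**What the plan says.** The blood pressure model is stated once, under Secondary Outcome Measurement in Phase 2: "linear mixed effects models to evaluate changes in blood pressure (dependent variable) according to time, group, and time x group interaction (independent variables". The Statistical Approach section adds no covariate, baseline constraint, covariance structure or small-sample method. There are two recordings, one before and one after the 8-week interval.

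On timing, the section on repeat monitoring says: "The procedures for ambulatory blood pressure monitoring are identical to those that were completed prior to randomization (see above". The section on the first recording says: "Following the baseline visit, all eligible and enrolled participants will be instructed to complete ambulatory blood pressure monitoring for 24 hours". The Randomization paragraph under Procedures says: "Following the completion of the baseline session, participants will be randomized to treatment group".

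On the stratum, Procedures describes assignment "using a stratified randomization approach (stratified by hypertension medication use", and Statistical Approach says: "Randomization will be stratified by hypertension medications (yes/no". Inclusion/Exclusion Criteria is conditional: "Randomization will be stratified based on antihypertensive medication use (yes/no), if necessary". The blood pressure model has no stratum term.

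On purpose, Sample size considerations says that, besides assessing feasibility and acceptability, the sample is "to provide a reasonable sample with which to estimate effect sizes and confidence intervals for secondary outcomes". Specific Aim 1 treats blood pressure as exploratory and unpowered. The monitoring sections are marked as suspended during the pandemic.

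**The concern.** Time, group and time x group together fit four free means, one per arm and visit. The baseline means of the two arms may therefore differ in the model, although in a randomized comparison with a pre-randomization baseline the true difference is zero. The model spends information on a quantity already known. With complete pairs its treatment estimate is the raw difference in mean change, which carries the full baseline noise of both arms.

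What is at stake is precision, not bias. For the secondary outcomes the plan promises effect sizes and confidence intervals, and Anticipated Outcomes says the results will inform a fully powered trial. With 15 women per arm, interval width is most of what this analysis can offer.

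**Working it through.** **Inputs.** From the documents: 30 women, 1:1, so n = 15 per arm; two recordings; model terms as quoted. Not in the documents, hence assumed: SD at baseline (SD1) and follow-up (SD2), their correlation rho, and the number of women with one or two recordings. The plan has no precision or power figure for blood pressure to reproduce; its only power statement concerns acceptability.

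**Step 1. Large-sample variances, complete pairs.**
- Planned model (difference in mean change): (2/n)(SD1² + SD2² - 2 rho SD1 SD2).
- Common baseline: (2/n) SD2²(1 - rho²).
- Saving, planned minus common baseline: (2/n)(SD1 - rho SD2)².

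The saving is never negative in large samples. It is zero when rho = SD1/SD2. With equal SDs the standard-error ratio is sqrt((1 + rho)/2).

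**Step 2. Small-sample penalty.** For the close alternative, baseline-adjusted ANCOVA at N = 30, the variance is multiplied by 1 + 1/(N - 4) = 1 + 1/26, and t with 27 df (2.052) replaces t with 28 df (2.048). The width factor is sqrt(1 + 1/26) x 2.0518/2.0484 = 1.021.

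**Step 3. Equal SDs, 30 pairs.** Width ratio = sqrt((1 + rho)/2) x 1.021. The half-widths are simulation means for the mixed models themselves (REML, unstructured 2 x 2 covariance, Kenward-Roger, SD 10 mmHg, 3,400 to 4,500 runs per cell).

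| rho | Width ratio by formula | Planned half-width (mmHg) | Common-baseline half-width (mmHg) | Narrower by |
|---|---|---|---|---|
| 0.3 | 0.823 | 8.76 | 7.17 | 18% |
| 0.5 | 0.884 | 7.42 | 6.54 | 12% |
| 0.6 | 0.913 | 6.62 | 6.01 | 9% |
| 0.7 | 0.941 | 5.76 | 5.39 | 6% |
| 0.8 | 0.968 | 4.68 | 4.51 | 4% (3% by formula) |
| 0.9 | 0.995 | 3.31 | 3.28 | 1% |

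Across the main simulated settings, Kenward-Roger coverage was 94.4-95.8% for the planned model and 94.2-95.7% for the common-baseline model without or with stratum terms. At rho 0.6 the gain is worth about 30/0.913² = 36 women instead of 30.

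**Step 4. Unequal SDs.** Take SD1 = 1 and rho = 0.6, and apply the factor 1.021.
- SD2 = 1.10: sqrt(0.7744/0.89) = 0.933; x 1.021 = 0.952, so 5% narrower.
- SD2 = 1.25: sqrt(1.0000/1.0625) = 0.970; x 1.021 = 0.990, so 1% narrower.
- SD2 = 0.80: sqrt(0.4096/0.68) = 0.776; x 1.021 = 0.792, so 21% narrower.

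At SD2 = 1.25 and rho = 0.8 = SD1/SD2 the large-sample ratio is exactly 1, and the small-sample factor leaves an interval about 2% wider.

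**Step 5. Incomplete data, equal SDs, rho 0.6.** With 20 pairs, 6 baseline-only and 4 follow-up-only women, half-widths are 7.94 (planned) and 7.12 (common baseline), so 10% narrower. With 12 pairs plus 6 and 4, they are 10.46 and 9.31. In that last setting Kenward-Roger coverage is 95.2% and 94.3%; without the correction it drops to 92.3% and 90.2%.

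**Step 6. Stratum terms.** With no stratum effect, 30 pairs and rho 0.6, adding stratum and stratum x time to the common-baseline model moves the half-width from 6.01 to 6.03. If medicated women (assumed 40%) differ by 8 mmHg at both visits, it moves from 6.14 to 6.06.

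**The case against.** The strongest reply is that nothing is wrong. The planned model holds its nominal coverage, answers the stated question about change, and feeds no decision rule. In mmHg the equal-SD gain is small: 0.37 at rho 0.7, 0.17 at 0.8 and 0.03 at 0.9. It also depends on SDs the documents do not give. Follow-up falls 8 weeks later in pregnancy, when new diagnoses and medications are expected, so equal SDs cannot be presumed. All of this stands. It limits the size of the claim but does not remove it, because the change needs no new data and precision is the stated purpose.

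A reader might infer three stronger criticisms that the documents do not support.
- **That omitting the stratum is a material fault.** Step 6 shows almost no effect either way. It would matter only if medication use predicted change, which the documents do not say. The conflict over whether stratification is conditional is a separate wording point.
- **That the first recording may follow randomization.** The sections on the first recording and on randomization are each tied only to the baseline visit, so neither states the order between them. But the repeat-monitoring section states it, the intervening blood-draw and ultrasound sections place those measures before randomization, and Table 1 lists 24-hour monitoring under Baseline.
- **That the planned model discards women with one recording.** A mixed model uses them; only the ANCOVA alternative drops them.

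**Conclusion.** The planned model is valid and could stand. A common-baseline model would usually give modestly narrower intervals: about 18% to 1% across rho 0.3 to 0.9 with 30 pairs and equal SDs. The benefit is not guaranteed. It is larger if the follow-up SD is smaller, shrinks if it is larger, and can become a loss of about 2% at N = 30 when rho is near SD1/SD2. The conclusion rests on the first recording preceding randomization and on assumed SDs and correlation. It would be wrong to read this as a finding of bias or invalid inference. Because blood pressure is exploratory and its measurement suspended, this is a low-priority efficiency gain.

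**What to change.** For each continuous blood pressure outcome, specify a mixed model with a common baseline mean: time and time x group, no baseline group effect, unstructured 2 x 2 covariance, Kenward-Roger intervals. Keep the planned model as a sensitivity analysis. With complete pairs, regressing follow-up on group and baseline is a close alternative. State in the section on the first recording that it precedes randomization, since the constraint is justified only then. Report how many women have paired and single recordings.

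Optionally add the medication stratum as a covariate if randomization was in fact stratified, and make Inclusion/Exclusion Criteria, Procedures and Statistical Approach agree on whether it is.

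The cost is SAP wording only. The downsides are the possible loss of about 2%, the reliance on the order of the first recording and randomization, and the need for the small-sample correction: without it, coverage falls to about 90% with 12 pairs.

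### The research-assistant calls ask about problems and discomfort only on mindfulness and record prenatal visits only on usual care, so neither item can be compared between arms

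*Combined protocol and SAP*

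**What the plan says.** Two adjacent paragraphs under Procedures describe the contact that each arm has with a research assistant.

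- Under Mindfulness Training Intervention + Treatment as Usual: "A research assistant will contact the participant between sessions to ask about any problem or discomfort participants might be experiencing". The sentence ties the question to the sessions and to the intervals between them, and adds "any problem or difficulty they are having attending prenatal care appointments". The interval is not stated, but "Mindfulness training sessions will occur once per week", so the contact is roughly weekly.
- Under Treatment as Usual: "A research assistant will check in with the participant each week to ask if they have been to any prenatal care appointments". Where she has, the assistant also records how many visits there were and how long each one lasted.

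Both arms receive the background care that the second call measures. The Randomization paragraph under Procedures says: "All participants will receive usual prenatal care, which may include intervention to prevent or treat hypertension during gestation".

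The Data and Safety Monitoring Plan covers all participants and sends to the IRB "Any adverse events, breaks of confidentiality, or any other data or safety issues that arise". It schedules no adverse-event question that is put to both arms.

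**The concern.** A call already exists in each arm, but the two calls collect different things. A woman who is asked regularly about discomfort will report more minor complaints than one who is not asked, even if both have the same complaints. A by-arm summary of such events would then reflect the asking as well as the training.

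The gap in visit data runs the other way. The amount of prenatal care is recorded only in the control arm, although it is the background treatment in both. The protocol plans to look for a signal in blood pressure between groups (Anticipated Outcomes) and to compare recurrence of hypertensive disorders, taken from chart review, across groups (Secondary Outcome Measurement). Chart diagnoses depend partly on contact with care. If contact differed between arms, the trial could not describe that difference beside those comparisons. Ambulatory monitoring is suspended during the pandemic, but chart outcomes are still to be collected.

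**Working it through.** The plan gives no figure to reproduce. The check sets out every scheduled source of these data by arm after randomization.

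| Item | Mindfulness | Usual care | Where |
|---|---|---|---|
| Call: problems or discomfort | Between weekly sessions | Not asked | Procedures, the two arm paragraphs |
| Call: difficulty attending prenatal care | Between weekly sessions | Not asked | Same |
| Call: prenatal visits, number and length | Not asked | Each week | Same |
| Preeclampsia symptom screen | 8 sessions + follow-up = 9 | Follow-up = 1 | Measures, Table 1 |
| New conditions, diagnoses, medications | Follow-up | Follow-up | Follow-up Visit; Measures |
| Repeated self-report scales | Follow-up | Follow-up | Measures, Table 1 |
| Hypertensive diagnoses, birth outcomes | Medical record | Medical record | Pregnancy Outcome Measures |

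The first three rows are one-sided. The last three are not limited to one arm. The list of items taken from the medical record does not include prenatal visits, so nothing fills the mindfulness gap in the third row. The preeclampsia screen is also uneven, but it is separate from the call script.

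**Volume of one-sided data.** Inputs: 15 women per arm (Specific Aim 1) and 8 weekly sessions. Assumptions: full attendance, one call in each interval between sessions, and usual-care calls for the same 8 weeks.

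- Discomfort enquiries: (8 - 1) x 15 = 105 on mindfulness, 0 on usual care. If every woman stopped after 4 sessions, the number in the feasibility criterion, and calls stopped too, the count would be (4 - 1) x 15 = 45 against 0.
- Woman-weeks with visit data: 8 x 15 = 120 on usual care, 0 on mindfulness.

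These count enquiries, not events.

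**Possible size of the artefact.** Let p be the true risk that a woman has at least one minor event, equal in both arms. Let c be the share of events captured on usual care relative to mindfulness. Expected women with a recorded event are 15p on mindfulness and 15pc on usual care, and the false risk difference is p(1 - c). Neither p nor c is in the documents; both are assumptions.

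- p = 0.40, c = 0.8: 6.0 against 4.8; difference 0.40 x 0.2 = 0.08.
- p = 0.40, c = 0.5: 6.0 against 3.0; difference 0.40 x 0.5 = 0.20.
- p = 0.40, c = 0.3: 6.0 against 1.8; difference 0.40 x 0.7 = 0.28.
- Extremes of the range examined: 0.20 x 0.2 = 0.04 and 0.60 x 0.7 = 0.42.
- c = 1 (equal capture): difference 0.

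**The case against.** A reader might infer that adverse events and exposure to usual care cannot be compared between arms at all. The documents do not support that. Follow-up collects emerging conditions, new diagnoses and new medications; depression, anxiety, sleep, PTSD and quality-of-life scales are repeated; and hypertensive diagnoses and birth outcomes come from the record. None of these is limited to one arm. Adverse events that come to light must be reported for any participant, so usual care would not record zero.

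A reader might also infer that the trial will report a false excess of adverse events. No by-arm adverse-event table is specified, and the aims contain no comparative safety objective. The mindfulness question is partly a check on how the training is tolerated, and discomfort during a session has no usual-care counterpart. This stands, but the question also reaches the time between sessions, when ordinary pregnancy complaints occur in both arms.

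Third, a reader might infer that the blood pressure and recurrence comparisons are confounded. Attendance arises after randomization. If the mindfulness package, calls included, changes attendance, that change is part of the effect of the package. The usual-care call may itself prompt attendance, so the direction of any difference is unknown. With 15 per arm, visit counts could not isolate that pathway, and the protocol says these comparisons are not powered for efficacy. What remains is descriptive: visit number and length in both arms would help a reader interpret the exploratory results.

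**Conclusion.** The point holds in a limited form. Two items are collected in one arm only by the stated design: minor problems solicited between visits, and prenatal visit number and length. Neither can be compared between arms. Any by-arm summary of minor events is liable to show an excess on mindfulness produced by asking. Under the assumed values that excess is 4 to 42 percentage points, and it falls to zero if capture is equal. The size therefore rests wholly on assumptions, while the asymmetry itself is in the text. A difference in prenatal contact could not be described alongside the blood pressure and recurrence comparisons.

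The primary outcomes (session attendance, home practice and the satisfaction score) do not depend on these calls. This is a minor, inexpensive improvement to the evidence passed to the later full trial.

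**What to change.** Use one research-assistant script on the same weekly schedule in both arms:

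1. New health problems or discomfort since the last call.
2. Prenatal visits attended, with number and length.
3. Any difficulty attending prenatal care.
4. Last, on mindfulness only, discomfort related to the training, tabulated separately.

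Base any between-arm comparison of adverse events on sources common to both arms: the common call questions, the follow-up interview and the medical record. This restricts the comparison only. Every adverse event should still be reported under the Data and Safety Monitoring Plan, whatever its source. Report prenatal visits descriptively for both arms.

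The cost is a revised call form and a minute or two more per call. The contacts and staff already exist in both arms. Answers to questions that were never asked cannot be reliably recovered later, so the change is worth making while women are still being followed.
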